8.4 Medical Case Manager “Step by Step” Document: (Integration of HepPSI PN roles)

1. **Meeting Client** (referral, community, phone call)
 - a. Introduce self, discuss MCM program and inquire if client is interested in enrolling into MCM program
 - b. Take down client's name, DOB, and contact information
 - i. *ask if it is okay to leave a voicemail/text message in order to provide a reminder for the scheduled appointment
 - c. Schedule an appointment to conduct MCM intake
 - d. Schedule a “future appointment” on the database to remind client of intake appointment
 - e. Input client intake information on work calendar
 - i. *invite Conference Room calendar to event to reserve the space
2. **Intake Appointment**
 - a. Introduce self, offer refreshments, build rapport, discuss Hepatitis Education Project as a non-profit agency, and discuss different programs (ex. MCM, DOC, POP, SSP, Advocacy)
 - b. Ask how client heard about HEP
 - c. Explain what Medical Case Management is/expectations of being in the program
 - d. State that today's appointment will be to fill out paperwork to be enrolled in MCM program
 - e. Inquire if the client has insurance and a PCP in order to see an overview of what the rest of the intake appointment will look like
 - f. Provide hepatitis C education
 - i. Inquire what the client already knows about hepatitis C
 - ii. Discuss hepatitis C basics (ex. what is hep C, transmission, treatment)
 - g. Go over MCM Intake documents
 - i. Client's Rights and Responsibilities
 - ii. Client Consent for Services
 - iii. Demographic Form
 1. After client has completed filling out demographic form, scan the form for answers that may prompt more discussion (ex. hep A/B vaccines, alcohol use, SSP needs, etc.)
3. **Insurance**
 - a. If client does not have insurance, help client sign up for insurance on Washington Health Plan Finder or refer client to a clinic that has Insurance Navigators on staff
 - i. Seattle Indian Health Board
 - ii. NeighborCare 45th St. Clinic
 - iii. *when scheduling an appointment at any of these clinics, ask to schedule an appointment on day where the insurance navigator will be there
4. **Linkage to Care**
 - a. Discuss whether the client would be interested in receiving treatment at a community pharmacy
 - i. **If no**, discuss where client would like to be seen
 1. Offer suggestions/referral to PCP's that are treating for hepatitis C
 2. Fill out HEP's Release of Information with chosen Clinic's information
 3. Fill out chosen Clinic's Release of Information with HEP's information
 4. Call clinic to schedule an appointment

- a. When calling to schedule an appointment at a PCP, request an appointment as a new patient and report that you have hepatitis C.
5. Provide client with HEP's fold over business card with appointment information in order to request appropriate lab work.

ii. **If yes**, please ask the client the following questions to assess if their medical care would be appropriate for treatment from a pharmacist.

1. Do you have HIV?
2. Do you have active hepatitis B?
3. Have you ever been diagnosed with liver cirrhosis, had a liver transplant, or had liver cancer?
4. Have you ever been diagnosed with kidney disease or had a kidney transplant?
5. Are you currently pregnant?
6. Have you ever been treated for Hep C before?

iii. If the client reports yes to any of the above conditions, please refer to section 4i above.
If the client reports no to all of the above conditions, please move to next section (4iv)

iv. fill out HEP's Release of Information with Kelley-Ross' information

1. Fill out Kelley-Ross' Release of Information with HEP's information
2. Inform client they can see by the pharmacist on [days/hours TBD] at HEP for HCV treatment if they'd like
3. Provide client with HEP's fold over business card with appointment information in order to request appropriate lab work.

b. ***** If client might be a candidate for HepPSI study and HCV treatment at Kelley-Ross*****
(HCV+, potential interest in receiving HCV treatment, likely recent IVDU)

- i. Ask if client would be interested in participating in a paid research study. Remind client that their answer will not affect whether they can be treated or where they would like to seek treatment.
 1. **If yes**, refer client to [name] and [name] for study screening
 - a. Study cell number: [contact]
 - b. Onsite at HEP: Days/hours TBD
 - c. Onsite at ETS: Mondays 8am-1pm

5. Database

- a. Input all demographic information into MCM/Testing database
- b. Write case note of intake with important information that was discussed
- c. Schedule a future appointment to remind client about appointment
- d. Schedule a follow-up appointment on when to check-in with client about doctor or pharmacy visit

6. Follow-up on Initial Appointment

- a. Follow-up with client after initial doctor or pharmacy visit and inquire how the visit went
- b. Ask when upcoming appointment will be either for further hepatitis C testing or discussion of results
- c. Input client appointment date in the MCM database as a reminder that the client will be having an appointment to prompt a reminder call/text and follow-up

7. Reminders & Follow-ups on Appointments

- a. When a client has an any type appointment, ask if the client would like a reminder call/text message about the appointment

- i. Appointments include: further hepatitis C related testing, liver ultrasound, liver biopsy, and pharmacy appointment
- b. Always follow-up with a client after their appointment to gather more information about their hepatitis C (ex. genotype, viral load, fibrosis score, etc.)

8. Client started treatment!

- a. Once the client has started treatment inquire on treatment information (ex. Medication prescription, start date, and # of weeks on treatment)
- b. Inquire when/what time the client will be taking the medication.
- c. Discuss the importance of taking medication the same time everyday

9. Check-ins on treatment

- a. Discuss adherence support with client
- b. Check-in with clients to see if they are experiencing any side effects.
- c. Inquire if there are any other upcoming appointments they may have

10. 4 week/8 week/End of Treatment Blood Draws

- a. Provide appointment reminders and post appointment follow-up to inquire on lab results
- b. Input lab result information on MCM database

11. After Treatment

- a. Congratulate client for finishing up treatment!
- b. SVR-12
 - i. Discuss with client if they can get hepatitis C again, after they have been cured.
 - ii. State that an “undetectable” hepatitis C viral load does not mean that the client is cured. Discuss the importance of getting SVR-12 (sustained virological response) is what determines if a client is cured. If the client’s results come back “undetectable” it means the client is cured
- c. Discuss Re-infection
 - i. Tell clients that there is no hepatitis C vaccine = no immunity to hepatitis C
 - ii. Inform clients that they can get re-infected from their own old blood before they cured. Advise clients to throw away any hygiene equipment (ex. Razors, clippers, toothbrushes, ect.) or anything that may have their old blood on it.
 - iii. Provide information on syringe exchange programs in order to pick up new clean sterile supplies.
 - iv. Avoid other people’s blood AT ALL COST! Discuss the importance of not sharing any injection supplies or personal care items that may be an exposure risk.
 - v. Encourage client to stay engaged with doctor to keep track of overall health.
- d. State that you will continue to follow-up with client until their SVR-12 appointment and results. Report that you will check-in on a monthly basis instead of normal check-in occurrences while client was on treatment

12. Monthly post treatment check-ins

- a. Schedule (3) future appointments for “monthly check-ins” with clients to ensure that you do not lose client contact while they are waiting for SVR-12
- b. Check-in with client about how they are feeling post treatment, if they need any additional services, extend invite to MMU and SSP, and discuss re-infection as often as possible
- c. Inquire when client’s SVR-12 appointment is

13. SVR-12

- a. When client has reached SVR-12, inquire on date and results.
- b. If client’s test results come back “undetectable” that means the client is cured!

- c. If client does not need any other support post SVR-12, close client case.

General Information

Primary Researcher(s):	[name], [name], [name], [name]
Collaborators:	[name], [name]
Project Title:	Evaluation of a community-pharmacy program for medications to treat and prevent HCV, opioid use disorders, overdose, and HIV among HCV-infected PWID.
Date:	July 11, 2022

Study Aims and Design

General Context / Purpose: *A general context for the study and the particular contributions of the project*

The opioid epidemic is a major public health crisis in the United States, leading to substantial morbidity and mortality related to the consequences of opioid use disorders and injection drug use, namely hepatitis C virus (HCV), HIV, and overdose. Yet, we are at a unique historical moment, as we possess effective medications that can improve and sustain the lives of people who inject drugs (PWID). Currently there are medications that can be prescribed to 1) cure HCV (directly-acting antivirals or DAAs), 2) prevent HIV infection (Pre-exposure Prophylaxis [PrEP]), and 3) treat/prevent overdose (naloxone and medications to treat OUD). Furthermore, there is an unprecedented opportunity to eliminate HCV, a disease that is transmitted through injecting drugs. However, achieving the goals of elimination will require better systems for allowing PWID access to medications to cure hepatitis C, as well as medications to prevent overdose and HIV. Pharmacists and community-pharmacy programs may be an innovative solution for this problem. Collaborative Drug Therapy Agreements (CDTAs) allow pharmacists to have authority to autonomously perform testing and prescribing and dispensing medications.

Aim(s): *The objective(s) of the analysis*

Aim 1: To conduct qualitative interviews with HCV-infected PWID to inform the development of a community-pharmacy program to expand access to medications to treat and prevent HCV, opioid use disorders, overdose, and HIV.

Aim 2: To pilot and evaluate a community-pharmacy program for medications to treat and prevent HCV, opioid use disorders, overdose, and HIV among HCV-infected PWID.

We will examine the following sub-aims:

1. The number/percent of participants who successfully link to the community pharmacy program and are seen for initial evaluation.

2. The number/percent who initiate medications for HCV.
3. Number/percent who receive other medications (naloxone, PrEP, and MOUD)
4. Baseline and 6-month follow-up substance use in past 30 days via modified Addiction Severity Index (ASI)
5. Baseline and 6-month follow-up the number of injecting episodes using shared needle/syringe within the past 30 days via the modified Risk Behaviors Survey (RBS)
6. Baseline and 6-month follow-up the number of episodes of unprotected vaginal or anal sex within the past 30 days via RBS
7. Self-reported participant Likert scale surveys of satisfaction and willingness to refer an injecting partner to the community pharmacy for treatment
8. The number/percent who complete treatment for HCV, defined as having received all planned medication doses.
9. SVR12 defined as undetectable HCV viral load at least 12-weeks post treatment completion

NOTE: This analysis plan does not include the data on injection network

Inclusion/Exclusion Criteria: *Defines the population to be analyzed. Describe criteria that were part of original data collection and additional criteria needed for this particular project.*

Inclusion criteria:

1. Age ≥ 18 years old
2. Injected any drug within the past 90 days (intravenous or intramuscular)
3. Tested positive for HCV (screening and/or confirmatory viral load) at a community testing site (syringe exchange programs, addiction treatment programs, homeless shelters, urban drop-in shelters and low-income housing sites)
4. HCV treatment naïve and not currently already receiving treatment
5. Willing to undergo evaluation for HCV at a community pharmacy

Exclusion criteria:

1. People who plan to leave the Seattle area within 6 months
2. Do not wish to be treated for their HCV infection
3. Are known to be pregnant
4. Report impending incarceration that would disrupt clinical care
5. Are not comfortable reading and speaking English
6. Report being HIV-positive
7. Report having end-stage renal disease or require dialysis treatments
8. Report prior enrolled in (i.e. completed at least the initial intake appointment) the Kelley-Ross pharmacy program for hepatitis C treatment ("One Step Hep C Free")

Data and Variables Needed for Analysis

Add rows to tables as needed

If a dataset or variable needs to be created / does not exist yet, you can note that here.

Variable Name	Definition	Variable type	Sub-aim #
m6hcvtxpharmd	Since our first visit, were you seen by the pharmacist (refer to them by name) for hepatitis C medications?	Yes/no	1
ehrtxkelleyross, ehrtxkrevaldoc (EHR)	Did this participant seek treatment through the KR community pharmacy program? (defined as presence of initial eval note by Kelley-Ross pharmacist)	Yes/no	1

Variable Name	Definition	Variable type	Sub-aim #
M6hcvpharmdmed	Since our first visit, did you take any medications to treat hepatitis C through the pharmacist ([name])? This can mean that you took only one pill, some of the pills, or all of the pills you were prescribed.	yes/no	2
M6hcvpharmdmedcom pno	If no, why not?	Check all that apply	2
M6hcvothpromed	Since our first visit, did you take any medications to treat hepatitis C through the provider ? This can mean that you took only one pill, some of the pills, or all of the pills you were prescribed.	Yes/no	2
ehrtxinitiate (EHR)	Was treatment initiated? (Defined as meds were prescribed, regardless of showing up to receive)	Yes/no	2
ehrtxwhynotinitiated (EHR)	Why was treatment not initiated? (Response options: ppt determined not appropriate for tx, ppt verbalized not wanting tx, ppt never returned, ppt did not complete workup, other (check all that apply))	categorical	2
M6hcvpharmdmedper cent	On a scale of 0% to 100%, how much of your medication did you take? Where taking every pill would be 100%, taking half the pills would be 50% and not taking any pills would be 0%. If you are still in your hepatitis C treatment course, think about how much of the medications you should have taken to date.	Integer, 0-100	8

M6hcvothpromedcom p	Have you completed your treatment regimen for hepatitis C(normally 8-12 weeks of daily medications)?	Yes/no	8
ehrtxiterrupt; ehrothxiterrupt (EHR)	Does the EHR text mention a treatment interruption?	Yes/no	8
ehrtxiterruptdays, ehrtxiterruptweek; ehrothxiterruptdays, ehrothxiterruptweek (EHR)	If yes, how many days? And at what week did the interruption occur?	Integer, -100, 1-12	8
ehrtxadherence (EHR)	Do the notes document non-adherence?	Yes/no	8
ehrtxdctx (EHR)	Did the provider pre-maturely discontinue treatment?	Yes/no	8
ehrrxreceived (EHR)	Did the participant ever pick-up/receive their medication from the pharmacist?	Yes/no	8
ehrrx1disptime (EHR)	Date of first medication dispensation	Date_mdy	8
ehrrx2actualdisptime (EHR)	Date of actual second medication dispensation	Date_mdy	8
ehrrx3actualdisptime (EHR)	Date of actual third medication dispensation	Date_mdy	8
m6hcvpharmdsrv12	Did you have a blood test to see if you were cured?	Yes/no	9
M6hcvothproccure	Has your provider told you that you are cured of hepatitis C?	Yes/no	9
m6hcvpharmdsrv12res ult	What were the results of that test?	Categorical	9
ehrlabavailable (EHR)	Are there post treatment HCV viral load lab results?	Yes/no	9
ehrlabresultdetect, ehrlabresultdetect2 (EHR)	Result (undetectable, detectable & quantifiable, detectable & unquantifiable)	Categorical	9

Descriptive/Other Variables of Interest (Baseline variables listed, 6-month follow-up variables start with "m6...":

Variable Name	Definition	Variable type	Sub-aim #
age	Age	continuous	NA
race	race	Categorical, nominal	NA

hispanic	Ethnicity/Hispanic/latinx	Yes/no	NA
gendid	Gender identity	Categorical, nominal	NA
Shstay	In the past 90 days, or since [des_neg90daycalc_2], where have you typically spent the night? *read options to participant, check all that apply	Discrete, check all that apply	NA
Shemploy	How would you describe your current employment status?	Categorical, nominal	NA
shinsur	Do you currently have health insurance or health care coverage?	Yes/no	NA
shinsurtype	What kind of health insurance or coverage do you currently have?	Categorical, nominal	NA
txsought	Prior to participating in this study, have you ever sought treatment for hepatitis C?	Yes/no	NA
othrxhivpos	have ever been told that you are HIV-positive?	Yes/no	NA
othrxnalox	Do you currently have Naloxone (i.e. Narcan), a medication to treat an overdose? It can be either on you right now, or at the place where you stay.	Yes/no	3
othrxoudrx	In the past 12 months, since [des_neg1yearcalc], which of these medications have you been prescribed and used as directed?	Categorical, nominal	3
Othrprepuse, or othrxprepnnow	Have you ever used PrEP? Or taking now?	Yes/no	3
*asi...	Variables for ASI substance use and injection drug use	ASI past 30 days Route Number of days	4
hivdayshare	How many times did you use a cooker/cotton/rinse water that had been used by another person who injects in the last 30 days?	Discrete, count between 0-30	5
hivshareafter	How many times did you share your works (needle/syringes) with somebody else after you used it in the last 30 days?	Discrete, count between 0-30	5
Hivinsertvagcond Hivinsertanalcond Hivreceptvagcond hivreceptanalcond	Episodes of sex without condom	Discrete, count between 0-30	6
M6pnexpplan	My navigator and I developed a plan for hepatitis C treatment.	Categorical, ordinal	7
M6pnexpunderstand	My navigator and I understand each other.	Categorical, ordinal	7
M6pnexpchange	We have established a good understanding of the kind of changes that would be good for me.	Categorical, ordinal	7

M6pnexpefficient	I believe the time my navigator and I are spending together is spent efficiently.	Categorical, ordinal	7
M6pnexpaccomp	My navigator understands what I am trying to accomplish.	Categorical, ordinal	7
M6pharmdexp	I had a positive experience with the pharmacist who saw me for hepatitis C.	Categorical, ordinal	7
M6pharmdexprecom	I would recommend the pharmacist to other people I know who inject drugs.	Categorical, ordinal	7
m6pharmdexpquest	The pharmacist addressed the healthcare concerns and questions that I brought up during our visit(s).	Categorical, ordinal	7
m6pharmdexphelp	The pharmacist was able to help me with the services I was seeking.	Categorical, ordinal	7
m6pharmdexpunderstand	The pharmacists were understanding of the difficulties I face trying to access healthcare.	Categorical, ordinal	7
m6pharmdexpwelcome	I felt welcomed in the setting where I saw the pharmacist.	Categorical, ordinal	7

Analytic Plan

Descriptive Analyses

First we will calculate participant demographic and HCV treatment characteristics using their baseline survey data (see Table 1). Then Compare participant opioid use disorder (OUD) and PrEP medications, injection drug use practices, and HIV risk behavior characteristics at baseline and final visit (Table 2). Figure 1 shows a Diagram of participant progress from pre-enrollment to end of treatment. Figures 2 and 3 are stacked bar charts showing the participant responses on pharmacist care and patient navigator satisfaction Likert scale survey questions at the final visit.

Inferential Analyses

McNemar's exact test for matched pairs or t-test to test for associations or difference in means between baseline and final visit (table 2).

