4.3.1 ASSESSMENTS OVERVIEW

The baseline survey will assess socio-demographics, substance use*, HIV risk behaviors*, and awareness of and interest in HCV treatment. After 6 months, participants will complete a follow-up (final) survey which will include information on:

- a) Whether an evaluation for HCV occurred at the community pharmacy or another site since the baseline visit
- b) Whether HCV treatment was initiated since baseline visit— assessed by self-report and pharmacy/medical records for confirmation.
- c) For patients who report that they have not been treated for HCV, reasons why (co-morbid conditions interfering, competing priorities, lack of interest, spontaneous clearance, etc.).
- d) Substance use*—measured by the modified Addiction Severity Index (ASI)(28)
- e) HIV Risk Behaviors*—measured by the modified HIV Risk Behaviors Survey (RBS)(29, 30)
- f) Receipt of naloxone, PrEP, and medications for OUD: self-report, confirmed with review of pharmacy record of dispensation/refills.
- g) Medication satisfaction, tailored to direct-acting antiviral treatment
- h) Medication adherence— assessed by record of medication pick-ups and also through self-report
- i) Injecting network (number of partners they have shared injected drugs with and, of those, how many they would be willing to refer to the site where they were treated)
- j) Completion of HCV Treatment – self-report and medical record chart review to assess if HCV treatment was fully completed.
- k) Sustain Virologic Response (SVR12) – Medical record review to assess obtainment of SVR12 results among participants who complete HCV treatment. For patients missing SVR12 results at the time of 6 month follow-up (either due to not yet having reached 12 post-treatment date or simply missing data), chart reviews will be conducted again up to 3 months after the 6 month follow-up.

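### The SAP's record variable for HCV treatment initiation counts a prescription whether or not it was collected, so it cannot confirm that treatment started

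*SAP*

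**What the plan says.** The SAP (Aim 2, sub-aim 2) names the outcome as "The number/percent who initiate medications for HCV". Unlike sub-aims 8 and 9, it carries no definition.

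The SAP variable table assigns two kinds of yes/no indicator to sub-aim 2:

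- **Self-report at 6 months:** `M6hcvpharmdmed` (through the pharmacist) and `M6hcvothpromed` (through another provider). Both ask about medication taken, with the gloss "This can mean that you took only one pill, some of the pills, or all of the pills you were prescribed".
- **Chart:** `ehrtxinitiate`, worded "Was treatment initiated? (Defined as meds were prescribed, regardless of showing up to receive".

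The table also holds two receipt items: `ehrrxreceived` ("Did the participant ever pick-up/receive their medication from the pharmacist") and `ehrrx1disptime`, the date of first dispensing. Both are tagged to sub-aim 8 (completion) only.

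Protocol 4.3.1(b) says initiation is "assessed by self-report and pharmacy/medical records for confirmation". For naloxone, PrEP and medications for opioid use disorder, 4.3.1(f) specifies "self-report, confirmed with review of pharmacy record of dispensation/refills". For adherence, 4.3.1(h) specifies "assessed by record of medication pick-ups and also through self-report".

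The SAP's Analytic Plan describes two tables, three figures and paired tests for Table 2. It does not say which source defines initiation.

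**The concern.** One outcome has two indicators that measure different events. A person who was prescribed medication but never picked it up is an initiator on the chart item and, answering truthfully, a non-initiator on the survey item. The chart item therefore cannot do the job 4.3.1(b) gives the records. It would even appear to confirm a mistaken survey answer from someone who never received any medication.

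The program exists to get medication to people who face barriers to care, and failing to collect is one such barrier. An initiation rate that counts it as success would flatter the model at that step. The protocol already relies on dispensing or pick-up records for other medications and for adherence, so HCV initiation has been given a weaker record than its neighbours.

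**Working it through.** **1. The plan's own figures.** Protocol section 6 gives exact binomial 95% intervals for n = 40. The Clopper-Pearson limits are the 0.025 quantile of Beta(x, n−x+1) and the 0.975 quantile of Beta(x+1, n−x).

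| x/40 | Protocol | Recomputed |
|---|---|---|
| 10 | 0.13–0.41 | 0.127–0.412 |
| 20 | 0.34–0.66 | 0.338–0.662 |
| 30 | 0.59–0.87 | 0.588–0.873 |

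All three reproduce. No stated number is wrong; the problem is one of definition.

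**2. One participant, prescribed but never supplied, answering truthfully.**

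| Item | Value | Tagged to sub-aim |
|---|---|---|
| `ehrtxinitiate` | yes | 2 |
| `M6hcvpharmdmed` | no | 2 |
| `ehrrxreceived` | no | 8 |
| `ehrrx1disptime` | empty | 8 |

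**3. When that person counts as initiated.** Let k be the number of uncollected prescriptions, and m (at most k) the number of those people whose 6-month survey is missing. The overstatement is d/40, where d is the number of non-collectors for whom the chart item decides.

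| Rule | d |
|---|---|
| Chart item alone | k |
| Either source suffices | k |
| Self-report, chart item filling in for a missing survey | m |
| Self-report decides | 0 |

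Each unit of d is worth 1/40 = 2.5 percentage points. Someone treated elsewhere who reports it is a genuine reported initiator and adds nothing to d.

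**4. Illustration.** The documents give no prescribing or collection counts, so everything here is assumed: 30 of 40 prescribed (a count borrowed from the protocol's interval examples), everyone supplied took at least one pill, nobody treated elsewhere, truthful answers. The chart item alone gives 30/40 = 75.0% (58.8–87.3). Actual initiation is (30−k)/40:

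| k | Actual initiation (exact 95% CI) | Overstatement, (k/40) × 100 |
|---|---|---|
| 0 | 30/40 = 75.0% (58.8–87.3) | 0 points |
| 2 | 28/40 = 70.0% (53.5–83.4) | 5 points |
| 4 | 26/40 = 65.0% (48.3–79.4) | 10 points |
| 6 | 24/40 = 60.0% (43.3–75.1) | 15 points |
| 10 | 20/40 = 50.0% (33.8–66.2) | 25 points |

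If the chart item only fills in for missing surveys, the reported rate at k = 4 is (26+m)/40: 65% for m = 0, 70% for m = 2 and 75% for m = 4.

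The interval around the reported 75% does not allow for this error, which runs in one direction only. At k = 10 the actual 50% lies below the interval's lower limit of 58.8%.

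**The case against.** The best defence is that 4.3.1(b) already puts self-report first and speaks of pharmacy and medical records generally, not of prescriptions. The receipt items are in the table, a sub-aim tag is not a derivation rule, and nothing forbids using them for sub-aim 2. That stands as far as it goes: an analyst could do the right thing. But the SAP assigns sub-aim 2 a chart item that defines initiation explicitly by prescription, and an analyst following the table would use it.

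Non-collectors are also not lost from view. They fail completion under sub-aim 8, and 4.3.1(c) collects, "For patients who report that they have not been treated for HCV, reasons why". Figure 1 is described but not shown and may already separate prescribed from received. These points limit the harm without correcting the initiation count.

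Initiation is descriptive in a 40-person single-arm pilot; no test or decision threshold rests on it. That stands, and it bears on severity.

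Two stronger readings are tempting. A reader might infer that the reported initiation rate will be too high. The documents do not support that: the error needs at least one uncollected prescription and a rule under which the chart item decides, and neither is stated. A reader might also add the swings that missing surveys could cause. Those would affect any survey-based 6-month outcome, rest wholly on assumed counts, and do not come from `ehrtxinitiate`. The silence on combining sources and on missing surveys is missing detail; the defect is the prescription-based definition.

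**Conclusion.** The point holds and should be fixed. For sub-aim 2 the record indicator measures prescribing, while the outcome and the self-report items concern treatment actually started, so it cannot supply the confirmation 4.3.1(b) calls for.

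The only size that follows from the documents is 2.5 percentage points per uncollected prescription at n = 40, and only where the chart item decides. It is zero if every prescription was collected or if truthful self-report decides. The 0 to 25 points tabulated above rest on assumed counts and are not a forecast. The primary outcome, evaluation in the pharmacy program, does not use this variable and is unaffected.

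**What to change.** **Pharmacy-treated participants**

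- Make the confirming record for sub-aim 2 *medication received*: `ehrrxreceived` = yes, or a date in `ehrrx1disptime`. Use the same record where the 6-month survey is missing.
- Report `ehrtxinitiate` separately as *prescribed*, over all enrolled participants. Show it in Figure 1 if the figure does not already separate prescribed from received.
- Keep self-report leading, and classify both kinds of disagreement in advance. Self-report yes without a receipt record is counted and shown as unconfirmed. Receipt with self-report no is not counted and is shown as received but not taken.
- Survey non-responders would be classified by receipt alone, a different standard from responders. Report the rate based on receipt alone for everyone as a sensitivity check.

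**Participants treated elsewhere**

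- Use `M6hcvothpromed`, confirm it from the other provider's records where the release of information allows, and report how many remain unconfirmed. Inclusion criterion 6 provides for such releases and the SAP lists chart items that appear to cover other providers (the `ehroth` group). However, protocol 4.2.1.1.2 names only two forms signed at enrolment, for the Hepatitis Education Project and the pharmacy, so access may be incomplete.

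**Cost**

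This needs SAP wording and a short note that it clarifies 4.3.1(b), with the use of receipt for missing surveys marked as an addition. No new data are needed for pharmacy-treated participants. For those treated elsewhere no dispensing item is listed, so confirmation means some extra chart review. The initiation rate may come out lower than the prescription-based one, and receipt still does not prove that the medication was taken.
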